8.3.1.2 Shifts

Each subject’s laboratory values will be classified according to whether the test result is “low” (below the lower limit of normal [LLN]), “normal” (within the normal range), “high” (above the upper limit of normal [ULN]). Shift tables will be constructed based on both the minimum and

maximum post-baseline values for each subject. Data collected from unscheduled visits will be included in the determination of the per subject minimum and maximum values. A separate table will be provided which summarizes the results of the shift tables in which the number and percentage of subjects with a shift to low (from normal, high, or unknown) and the number of subjects with a shift to high (from normal, low, or unknown) will be tabulated; percentages will be based on the number of subjects at risk. The number at risk for a shift to low (high) is the number of subjects whose baseline value was not low (high), including unknown, who had at least one post-baseline value. Only directions of change indicating a clinical concern will be included in this table summarizing the shifts. The direction of concern is provided in [Table 1](#).

Table 1: Direction of Change Indicating Clinical Concern for Laboratory Tests

Laboratory Test	Direction	Laboratory Test	Direction
Chemistry		Hematology	
Liver		White blood cells	Low and High
ALT/SGPT	High	Lymphocytes	Low and High
AST/SGOT	High	Neutrophils	Low and High
Alkaline phosphatase	High	Monocytes	Low and High
Total bilirubin	High	Eosinophils	Low and High
Renal		Basophils	Low and High
Blood urea nitrogen	High	Red blood cells	Low and High
Creatinine	High	Hemoglobin	Low and High
Electrolytes		Hematocrit	Low and High
Sodium	Low and High	Platelets	Low and High
Potassium	Low and High		
Chloride	Low and High		
Other			
Glucose	Low and High		
Total protein	Low and High		

8.3.1.3 Potentially Clinically Significant Laboratory Abnormalities

Abnormal laboratory values will also be evaluated by determining the number and percentage of subjects with at least one potentially clinically significant laboratory abnormality over the course of the study that also represents a worsening from baseline. The potentially clinically significant levels are based on Grade 2 or higher thresholds from the Common Toxicity Criteria for Adverse Events (CTCAE v 4.02 2009) where possible, or were defined by Bioverativ’s Safety and Benefit Risk Management group. Subjects who have a post baseline laboratory value that meets the criteria for being potentially clinically significant but do not have a baseline value will be included in the numerator for determining the percentage of subjects with an abnormality. Percentages will be based on the number of subjects with at least one post baseline value for the given laboratory test. Threshold levels for potentially clinically significant laboratory abnormalities are provided in [Table 2](#) (hematology) and [Table 3](#) (chemistry). Data collected from unscheduled visits will be included in this analysis.

Table 2: Threshold Levels for Potentially Clinically Significant Hematology Abnormalities

Subjects from study 998HB102		
	Low	High
White blood cells	$<3.0 \times 10^9/L$	$\geq 16 \times 10^9/L$
Lymphocytes	$<0.8 \times 10^9/L$	$>12 \times 10^9/L$
Neutrophils	$<1.5 \times 10^9/L$	$>13.5 \times 10^9/L$
Monocytes	NA	$>2.5 \times 10^9/L$
Eosinophils	NA	$>1.6 \times 10^9/L$
Basophils	NA	$>1.6 \times 10^9/L$
Hemoglobin	$\leq 115 \text{ g/L}$	$\geq 190 \text{ g/L}$
Hematocrit	$\leq 37\%$	$\geq 60\%$
Platelet count	$\leq 75 \times 10^9/L$	$\geq 700 \times 10^9/L$
Subjects from study 9HB02PED		
	Low	High
Neutrophils	$<1.5 \times 10^9/L$	NA
Eosinophils	NA	$>1.6 \times 10^9/L$
Hemoglobin	$<100 \text{ g/L}$	Increase in $>20 \text{ g/L}$ above ULN
Hematocrit	$<30\%$	$\geq 60\%$
Platelet count	$\leq 75 \times 10^9/L$	$\geq 700 \times 10^9/L$

NA = not applicable

Table 3: Threshold Levels for Potentially Clinically Significant Chemistry Abnormalities

Subjects from study 998HB102		
	Low	High
Liver		
ALT/SGPT	NA	$\geq 3 \times \text{ULN}$
AST/SGOT	NA	$\geq 3 \times \text{ULN}$
Total bilirubin	NA	$\geq 34.2 \mu\text{mol/L}$
Renal		
Blood urea nitrogen	NA	$\geq 10.7 \text{ mmol/L}$
Creatinine	NA	$\geq 176.8 \mu\text{mol/L}$
Electrolytes		
Sodium	$\leq 126 \text{ mmol/L}$	$\geq 156 \text{ mmol/L}$
Potassium	$\leq 3 \text{ mmol/L}$	$\geq 6 \text{ mmol/L}$
Chloride	$\leq 90 \text{ mmol/L}$	$\geq 118 \text{ mmol/L}$
Other		
Glucose	$\leq 2.22 \text{ mmol/L}$	$\geq 9.71 \text{ mmol/L}$
Total protein	$\leq 45 \text{ g/L}$	$\geq 100 \text{ g/L}$
Subjects from study 9HB02PED		
	Low	High
Liver		
ALT/SGPT	NA	$>3 \times \text{ULN}$

AST/SGOT	NA	>3 × ULN
Total bilirubin	NA	>1.5 × ULN
Renal		
Creatinine	NA	>1.5 × ULN
Electrolytes		
Chloride	≤90 mmol/L	≥118 mmol/L
Other		
Glucose	<3.1 mmol/L	>8.9 mmol/L
Total protein	≤45 g/L	≥100 g/L

NA = not applicable, ULN = upper limit of normal

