8. SAFETY ANALYSIS

Safety data will be summarized for subjects from study 9HB02PED and subjects from study 998HB102, along with the overall total. The analysis population for safety analyses is defined in Section 4.3.

Adverse events (AEs) will be summarized for subjects from each parent study and overall for all subjects in study 9HB01EXT, regardless of treatment arm for subjects from study 998HB102, age cohort for subjects from study 9HB02PED, and treatment regimen in study 9HB01EXT.

In addition, all data from study 9HB01EXT will be provided in data listings.

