8.3.1. Hematology and Chemistry

All summaries will be structured such that the hematology and chemistry tests are presented in the order shown in the tables provided in Section 8.3.1. Hematology and chemistry evaluations taken during major surgical/rehabilitation periods will not be included in the summary but will be included in the listings and flagged.

Hematology measurements that will be collected and listed include white blood cell count (WBC), differential, hemoglobin, hematocrit, and platelet count.

Chemistry measurements that will be collected and listed include electrolytes (sodium, potassium, and chloride), glucose, total protein, total bilirubin, alanine aminotransferase (ALT), aspartate aminotransferase (AST), alkaline phosphatase (ALP) [collected for subjects from study 998HB102 only], blood urea nitrogen (BUN), and serum creatinine.

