Summary of enrollment by country and site
Summary of subjects attending each visit
Summary of demographic and baseline characteristics
Summary of medical and surgical history
Summary of concomitant medications
Summary of major protocol deviations
Summary of major protocol deviations based on EPD data in the original pre-change state
Summary of exposure
Summary of exposure by EPD entry compliance
Summary of last prescribed dose and dosing frequency
Summary of changes in study 9HB01EXT treatment regimens
Summary of prophylactic dose (IU/kg)
Summary of prophylactic dosing interval
Summary of annualized rFIXFc consumption (IU/kg)
Summary of bleeding episodes
Summary of annualized bleeding rate
Summary of annualized bleeding rate by type of bleeds
Summary of annualized bleeding rate by location and type of bleeds
Summary of annualized bleeding rate by the presence of target joints at screening in parent study
Summary of annualized bleeding rate by EPD entry compliance
Summary of subject's assessment of response to rFIXFc injections for the treatment of bleeding episodes
Summary of number of injections required for resolution of a bleeding episode
Summary of dose (IU/kg) of rFIXFc for resolution of bleeds
Summary of number of days from the last prophylaxis injection to a spontaneous bleeding episode
Summary of time (hours) between first and second injection to treat a bleeding episode
Summary of time (hours) between first and second injection to treat a bleeding episode by type of bleed
Summary of results and change from study 9HB01EXT baseline: CHO-KLAT total score from the Child Self-report Questionnaire
Summary of results and change from study 9HB01EXT baseline: CHO-KLAT total score from the Parent/Proxy Questionnaire
Summary of results and change from study 9HB01EXT baseline: Hemo-Sat total score and subscores
Summary of EQ-5D-Y descriptive system
Summary of results and change from study 9HB01EXT baseline: EQ-5D-Y visual analogue scale
Summary of hemophilia-related health-economic parameters
Summary of health economic parameters for all physician and emergency room visits
Summary of results and changes from study 9HB01EXT: Hemophilia Joint Health Score (HJHS)

Overall groups of subjects in 9HB01EXT

Summary of Physician's global assessment of the subject's response to his rFIXFc regimen

Summary of compliance for the treatment of bleeding episodes
Summary of prophylactic dose compliance
Summary of prophylactic dosing interval compliance

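### On 12 of 30 rows of the potentially clinically significant laboratory tables, 9HB02PED subjects have no limit but stay in the denominator, so the overall percentage on those rows is diluted

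*SAP*

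**What the plan says.** SAP 8.3.1.3 counts "subjects with at least one potentially clinically significant laboratory abnormality over the course of the study that also represents a worsening from baseline". The cut-offs that define such an abnormality come from Tables 2 and 3: "Threshold levels for potentially clinically significant laboratory abnormalities are provided in" those two tables. Each table has one block headed "Subjects from study 998HB102" and another headed "Subjects from study 9HB02PED", and the blocks do not list the same tests.

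The denominator has its own rule in the same section: "Percentages will be based on the number of subjects with at least one post baseline value for the given laboratory test". It makes no exception for a subject whose parent-study block has no limit for the test. Being specific to this analysis, it takes precedence over the general rule in SAP 5.2.2.

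Pooling is explicit. SAP 8 states: "Safety data will be summarized for subjects from study 9HB02PED and subjects from study 998HB102, along with the overall total". The list of tables puts the PCS hematology and chemistry summaries under "Overall groups of subjects in 9HB01EXT".

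On which tests children have, SAP 8.3.1 marks a single chemistry test as restricted to one parent study: "alkaline phosphatase (ALP) [collected for subjects from study 998HB102 only". ALP has no PCS limit in either block.

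**The concern.** A percentage is meaningful only if everyone in the denominator could have been counted in the numerator. Where a child has a potassium result, say, but no potassium limit, that condition fails in the overall column. A reader of the overall total would take the figure as the rate among all subjects with a potassium result, when only the 998HB102 subjects were graded.

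The pediatric column has a related problem of display. If a count of 0 is printed on such a row, it means that nobody was graded, but it could be taken to mean that no abnormality was seen.

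Long-term safety is the primary objective, and these tables are the summary meant to pick out the more important laboratory changes. The SAP takes more care in the section just before: the shift summary in 8.3.1.2 bases its percentages on subjects at risk of the shift in question.

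**Working it through.** The plan gives no figure of its own here, so the check is a count of limits followed by a ratio.

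**Step 1. Count the limits (SAP Tables 2 and 3, each Low or High cell that is not NA).**

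| Block | Hematology | Chemistry | Total |
|---|---|---|---|
| 998HB102 | WBC 2, lymphocytes 2, neutrophils 2, monocytes 1, eosinophils 1, basophils 1, hemoglobin 2, hematocrit 2, platelets 2 = 15 | ALT 1, AST 1, bilirubin 1, BUN 1, creatinine 1, sodium 2, potassium 2, chloride 2, glucose 2, total protein 2 = 15 | 30 |
| 9HB02PED | neutrophils 1 (low), eosinophils 1, hemoglobin 2, hematocrit 2, platelets 2 = 8 | ALT 1, AST 1, bilirubin 1, creatinine 1, chloride 2, glucose 2, total protein 2 = 10 | 18 |

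Every 9HB02PED pair also occurs in the 998HB102 block, so 30 − 18 = 12 pairs have no pediatric limit.

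- Hematology (7): WBC low and high, lymphocytes low and high, neutrophils high, monocytes high, basophils high.
- Chemistry (5): BUN high, sodium low and high, potassium low and high.

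**Step 2. Compare cut-offs on the 18 shared pairs.**

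- Same (9): neutrophils low, eosinophils high, hematocrit high, platelets low and high, chloride low and high, total protein low and high.
- Different (9): hemoglobin low and high, hematocrit low, ALT, AST, bilirubin, creatinine, glucose low and high. For ALT and AST the only difference is ≥ against >.

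**Step 3. Dilution on the 12 pairs.** Let x be the number of 998HB102 subjects counted, N₁ the 998HB102 subjects with a result and N₂ the 9HB02PED subjects with a result. As written, the overall percentage is x/(N₁ + N₂); among graded subjects it is x/N₁. The ratio is N₁/(N₁ + N₂), whatever x is.

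| N₁ | N₂ | Source of sizes | Ratio | Relative understatement |
|---|---|---|---|---|
| 100 | 20 | planned sizes, SAP 3.3.1 | 100/120 = 0.833 | 16.7% |
| 100 | 26 | 26 planned in 9HB02PED, Protocol 5.1.3 | 100/126 = 0.794 | 20.6% |
| 123 | 20 | 123 treated in 998HB102, Protocol 5.1.3 | 123/143 = 0.860 | 14.0% |

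Illustration with an assumed count of 5: 5/100 = 5.0% among graded subjects, but 5/120 = 4.2% in the overall column.

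**The case against.** The strongest reply is that little is lost. SAP 5.1 separates the two cohorts by default because they differ in age, and SAP 8 puts a 998HB102 column beside the overall total, so the undiluted percentage is in the same table. That is right. It confines the error to the overall column but does not remove it, because SAP 8 requires that column.

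Second, the table shells are not in the documents. Tables 2 and 3 leave seven tests out of the pediatric block and mark neutrophils high as NA, so the pediatric cells may well be printed as NA or omitted. Even if a 0 is printed, SAP 5.2.2 suppresses its percentage. A reader might infer that the tables will report 0% for children, and the documents do not support that. A shell showing NA would still leave the overall denominator unchanged.

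Third, a reader might infer that pediatric abnormalities on these criteria are all missed. That does not follow: without a pediatric limit there is no defined PCS event to miss, and which tests to grade in children is a clinical choice. The values also appear in the change-from-baseline summaries, the shift tables (SAP Table 1 covers all the tests concerned) and the normal-range listings.

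Fourth, Protocol 14 limits assessments to those made in the parent study. If 9HB02PED did not measure a test, its subjects have no result, leave that denominator, and the ratio becomes 1. This stands as a caveat. However, SAP 8.3.1 flags only ALP in this way, and neutrophils high is affected on any reading because children are graded for neutrophils low.

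Finally, the analysis is descriptive, and the primary endpoint, inhibitor development, is untouched. That limits the weight of the point.

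**Conclusion.** The point holds for the overall-total percentage on 12 of the 30 rows. There the stated rule includes subjects who cannot be counted, and the percentage is about 0.83 of the graded percentage at the planned sizes, with an assumed range of 0.79 to 0.86. The calculation assumes that every subject in both cohorts has a post-baseline result for the test. The documents give no event rates, so the absolute difference is unknown. Where a pediatric count of 0 is printed on these rows, it would mean not graded.

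Two broader readings should be resisted. The overall percentages are not too low in general: the other 18 rows are not diluted and the 998HB102 column is correct throughout. Nor are children graded on the same limits on those 18 rows: 9 use a different cut-off, so the overall figure there mixes two definitions, which is a matter for a footnote. This is a modest, inexpensive correction to two supportive safety tables and does not affect the study's main conclusions.

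**What to change.** In SAP 8.3.1.3, replace the denominator rule with wording such as: *the denominator is the number of subjects who have a post-baseline result for the test and for whose parent study Table 2 or Table 3 defines a limit for that test and direction.* Then:

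- show the 12 pairs as not evaluated in the 9HB02PED column;
- footnote that the overall figure on those rows rests on 998HB102 subjects only, or omit it there, since it would repeat the 998HB102 column;
- footnote that cut-offs differ by parent study on 9 of the 18 shared pairs.

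Whether to add pediatric limits is for the sponsor to decide; the correction does not depend on it.

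The cost is one SAP sentence, the footnotes and a small programming change, with no new data. The downside is that the overall denominator will differ between rows and some overall percentages will be slightly higher.

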8.3.2. Inhibitor Development

Inhibitor results of the Nijmegen-modified Bethesda Assay from the central laboratory will be listed. Results from blood samples collected during surgical/rehabilitation periods for the purpose of determining the presence of an inhibitor will be included.

A positive inhibitor occurs where a subject has a value ≥ 0.6 Bethesda Units (BU/mL) confirmed on re-testing between 2 and 4 weeks later. Both tests must be performed by the central laboratory.

A “low” titer inhibitor occurs where a subject has a value between 0.6 and <5.0 Bethesda Units (BU/mL) confirmed on re-testing between 2 and 4 weeks later.

A “high” titer inhibitor occurs where a subject has a value ≥ 5.0 Bethesda Units (BU/mL) confirmed on re-testing between 2 and 4 weeks later.

8.3.3. Incidence of Anti-rFIXFc Antibodies

The development of anti-rFIXFc antibodies will be assessed as the number and percentage of subjects negative throughout the study, positive at any time following study 9HB01EXT baseline, and positive at the final evaluation. Percentages will be based on the number of subjects who are antibody negative at study 9HB01EXT baseline and have one or more post-baseline antibody result in study 9HB01EXT.

In addition, the number of subjects who had the first positive evaluation within 13-week intervals will be summarized. The interval calculation will start from 9HB01EXT Study Day 1.

Results from blood samples collected during surgical/rehabilitation periods for the purpose of determining the presence of anti-rFIXFc antibodies will be included in this analysis.

A listing of anti-rFIXFc antibody results will be provided.

8.4. Vital Signs

Vital signs (systolic and diastolic blood pressure, pulse, respiratory rate, and oral temperature) will be summarized for the observed values and change from baseline using descriptive statistics by visit and for overall treatment regimen for the Safety Analysis Set.

The number and percentage of subjects with clinically relevant post-baseline abnormalities will be presented. The criteria for clinically relevant post-baseline abnormalities are shown below in Table 4.

Results taken during major surgical/rehabilitation periods will not be included in the analysis.

Table 4 Criteria to Determine Clinically Relevant Abnormalities in Vital Signs

Vital Sign	Criteria for Abnormalities
Temperature	>38°C and an increase from pre-dosing of at least 1°C
Pulse	>120 beats per minute post-baseline, or an increase from pre-dosing of more than 20 beats per minute, or <50 beats per minute post-baseline, or a decrease from pre-dosing of more than 20 beats per minute
Systolic Blood Pressure	>180 mmHg post-baseline, or an increase from pre-dosing of more than 40 mmHg, or <90 mmHg post-baseline, or a decrease from pre-dosing of more than 30 mmHg
Diastolic Blood Pressure	>105 mmHg post-baseline, or an increase from pre-dosing of more than 30 mmHg, or <50 mmHg post-baseline, or a decrease from pre-dosing of more than 20 mmHg

A listing of all vital signs plus height and weight will be provided, including data recorded at unscheduled visits and during surgical/rehabilitation periods. Vital signs collected during surgical/rehabilitation periods will not be included in the summary but will be included in the listings and flagged.

9. Sensitivity Impact Assessment

As proposed under the MHRA CAPA commitment, an analysis will be performed to assess the impact of the EPD query process and addition of manually created records on the results of study 9HB01EXT. The analysis will include summary tables that will be re-run plus any additional summary tables or listings required for inclusion in the final clinical study report (CSR).

Background

Subject recorded diary data was queried via a defined process which originally required confirmation with the subject of **all** changes. Subsequently, it was identified that this did not occur in all cases nor was this actually necessary for all types of change. In 2014, it was agreed that only certain categories of changes required subject confirmation, and a process implemented to ensure adequate documentation to support those changes was available. After a subsequent MHRA audit in 2015, further consideration was given to the timing of changes relative to the actual data generation, reliable subject recall period, and still lack of appropriate documentation to support changes in all cases. Therefore, taking into consideration these findings and industry standards to limit changes of subject reported data, the query process was updated to **only allow changes defined as not requiring subject confirmation**. Although changes classified as SVC/L60 did not require subject confirmation (as agreed with MHRA in 2014), these changes will no longer be made directly into the data, but will be applied via a programmatic data convention (details described in Section 5.4).

The Total Query Report (TQR) documents all changes to the EPD data. The changes in this report were classified according to a pre-defined list (see table below).

Code	Description	Requires subject confirmation
LN	Minor lot # change (addition/deletion of spaces or hyphens) and Major lot # change (any other changes to lot #)	N
D/EPD	Duplicate entry in EPD by subject - deleted	Y
D/CRF	Entry in EPROLOG is also in CRF/INFORM as in-clinic dose	N
Dose	Vials added or removed	Y
SVC	Single vials combined - entered as separate injections in error	Y
SVC/L60	Single vials combined - entered as separate injections in error – injection time range for combined records is ≤ 60 mins	To be applied via programmatic data convention during analysis as described in Section 5.4
Error	Subject entered in error - entry deleted	Y
DTOI	Date and/or time of injection corrected	Y
Pre-Fc	Entries deleted as prior to first dose with Fc (not required per protocol)	N
Train	Entries deleted as training/prior to first dose with Fc (not required per protocol)	N
Test subject	Subject does not exist - entries deleted	N

Code	Description	Requires subject confirmation
Inj Reason	Reason of injection changed (other than routine prophylaxis or other to surgical prophylaxis if a confirmed minor/major surgery or procedure is capture in the eCRF during the defined surgical period or date of procedure; or from new bleed to follow up)	Y
Inj Reason Surgery	Injection reason from routine prophylaxis or other to surgical prophylaxis	N
BLD LOC	Change in Bleed Location	Y
BLD TYP	Change in Bleed Type	Y
BLD SYM	Change in Bleed Symptoms	Y
DTOB	Date and/or time of bleed corrected	Y
Activity	Change in Physical Activity question	Y
TRT SD	Amendment to Treat with Study Drug item: "Did you inject with rFIXFc (Study Drug)?"	Y
TRT BLD	Amendment to Treat Bleed item: "How did the bleed respond to injection on ..."	Y
Abandon	Query request was raised but then cancelled by site	N
In-clinic administration	In-clinic administration entered in EPD and corrected in reference to source records	N
NBTFU	Injection to treat the bleed is < 72 h of the previous injection to treat the existing bleed New bleed deleted, follow up inj to existing bleed added (per protocol definition)	N
Tx Arm/Reg	Change in treatment arm or regimen	N
ADMIN	Changes made by site to data fields that the site would have entered originally and/or are administrative. E.g. study name or data entered into an incorrect field and corrected, data entered that is not required, expiry date of IMP extended, data field changes that are duplicated due to multiple site staff involved in the query process or similar, correction of injection reason related to treatment arm, e.g. routine prophylaxis to weekly dose for subjects on a weekly regimen	N (However, for some types of issues are applied via programmatic data convention during analysis as described in Section 5.4)

In certain circumstances, where subjects could not enter records directly into the EPD for any reason, records were requested to be created manually by the site according to a pre-defined documented process which included SDV by CRA. However, it was subsequently identified that confirmation of SDV could not be provided. Records were re-SDVed at site to determine whether source was available, or whether contemporaneous documentation of confirmation with the subject was available. *(Not discussed further in this SAP).*

For the impact assessment, all data record changes requiring subject confirmation will be set back to the original values. Manually created data without complete SDV of the record will be

considered unsupported by SDV at site, and will be removed for the purpose of the impact assessment.

SDTM and ADAM datasets will be re-created and certain statistical analyses re-run. Endpoints covered under the impact assessment include:

- exposure
- annualized number of bleeding episodes per subject (ABR)
- subject’s assessment of response to treatment with rFIXFc for bleeding episodes
- number of injections and dose per injection of rFIXFc required to resolve a bleeding episode
- prophylactic dose and dosing interval

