16. STATISTICAL METHODS AND DETERMINATION OF SAMPLE SIZE

In general, subjects who enroll into study 9HB01EXT from any rFIXFc parent study will have their parent study data integrated with their data from 9HB01EXT. A parent study is defined as a study where subjects may be enrolled into 9HB01EXT after study completion or at a time specified in the protocol. .

All statistical analyses will be descriptive in nature. No formal comparison is planned and no hypothesis will be formally tested. Continuous variables will be summarized and presented by number, mean, median, standard deviation, minimum and maximum, and, where appropriate, with the 25th and 75th percentiles. Categorical variables will be summarized by the number and percentage in each category.

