5.1. General Principles

The following rules will be followed for all applicable analyses contained in this SAP, unless specified otherwise.

Because the subjects from study 998HB102 and study 9HB02PED are in different age groups (i.e., ≥ 12 years of age for study 998HB102 and < 12 years of age for study 9HB02PED) and may therefore have different safety and efficacy profiles, analyses will be performed separately for subjects from study 998HB102 and for subjects from study 9HB02PED.

For subjects from study 9HB02PED, age cohort (< 6 years old and 6 to < 12 years old) is taken from study 9HB02PED.

Summaries of study 9HB01EXT data will be produced using standard summary statistics. Listings will also only include data from study 9HB01EXT and the treatment regimen associated with each data point, unless specified otherwise. Data collected at unscheduled visits will be included in the definition of the maximum and minimum post-baseline values.

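### For pulse and blood pressure, SAP Table 4 uses one set of absolute limits for all ages and counts values that have not changed from baseline

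*SAP*

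**What the plan says.** SAP 8.4 plans the number and percentage of subjects with an abnormal vital sign after baseline: "The criteria for clinically relevant post-baseline abnormalities are shown below in Table 4". Table 4 is a single table with no split by age or parent study.

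For three signs, the absolute limit and the change criterion are alternatives:

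- Diastolic pressure, low side: "<50 mmHg post-baseline, or a decrease from pre-dosing of more than 20 mmHg".
- Systolic pressure, low side: "<90 mmHg post-baseline, or a decrease from pre-dosing of more than 30 mmHg".
- Pulse, high side: ">120 beats per minute post-baseline, or an increase from pre-dosing of more than 20 beats per minute".

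Temperature needs both parts: ">38°C and an increase from pre-dosing of at least 1°C".

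The change criteria refer to the pre-dosing value, not to the study baseline. The protocol schedule (footnote 5) has vital signs taken before and after injection at dosing visits.

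For laboratory tests, SAP 8.3.1.3 counts a subject only for an "abnormality over the course of the study that also represents a worsening from baseline", and its Tables 2 and 3 list thresholds separately for subjects from 998HB102 and from 9HB02PED. SAP 5.1 says the two age groups "may therefore have different safety and efficacy profiles". SAP 8 shows safety results for each parent study and in total.

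**The concern.** Two features of the pulse and blood-pressure criteria do not fit the rest of the SAP.

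First, a value beyond the limit counts whether or not it was already there at the start of the extension. This applies at every age. The list of tables titles the output as clinical abnormalities from the 9HB01EXT baseline, so a reader will take the percentage as something that arose during the extension.

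Second, the same fixed limits apply to adults and to children who entered the parent study before age 6. The SAP allows for age elsewhere: by parent study for laboratory thresholds, by age at entry for the joint score (4 years or older, SAP 7.4.4) and for the questionnaires (SAP 7.5). The joint-score restriction suggests that children under 4 at extension entry were foreseen. Table 4 has no such provision.

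At stake is the meaning of the 9HB02PED column and of the total in one safety table, in a study whose primary objective is long-term safety.

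**Working it through.** The plan states no expected rate for this table, so there is no figure to reproduce.

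**Step 1: Table 4 as written, with zero change.** Each criterion was applied with the post-baseline value equal to the earlier value.

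| Sign | Unchanged values counted | Unchanged values not counted |
|---|---|---|
| Diastolic (mmHg) | 45, 48, 49 | 50, 60 |
| Systolic (mmHg) | 85, 88, 89 | 90, 110 |
| Pulse (bpm) | 49, 121, 125 | 50, 100, 120 |
| Temperature (°C) | none | 36.5, 38.0, 38.5 |

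Three of the four signs count a subject whose value has not moved; temperature does not. This follows from the text alone.

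**Step 2: the SAP's other rules.**

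| Analysis | Subject already abnormal at baseline | Limits by parent study |
|---|---|---|
| Laboratory abnormalities (8.3.1.3) | counted only if worse than baseline | yes |
| Laboratory shift summary (8.3.1.2) | not at risk for that direction | not applicable (normal range) |
| Anti-rFIXFc antibodies (8.3.3) | excluded from the denominator | not applicable |
| Pulse and blood pressure (8.4) | counted, even if unchanged | no |

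**Step 3: possible size in children, by assumption only.** Take diastolic pressure as Normal with mean m and SD s. For readings in whole mmHg:

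- per reading, p = Φ((49.5 − m)/s);
- ever flagged over 8 independent visits (six-monthly for up to 4 years), 1 − (1 − p)^8.

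Example with m = 60, s = 9: (49.5 − 60)/9 = −1.167, so p = 0.122 and 1 − 0.878^8 = 0.65.

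The last column is a simulation with between-child SD 6.5 and within-child SD 6.2. The total SD is √(42.25 + 38.44) = 9.0 and the correlation between visits is 42.25/80.69 = 0.52.

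| Assumed mean (mmHg) | p per reading, SD 7 to 11 | Ever flagged, independent | Ever flagged, correlated |
|---|---|---|---|
| 52 | 0.36–0.41 | 0.97–0.99 | 0.80 |
| 55 | 0.22–0.31 | 0.86–0.95 | 0.67 |
| 60 | 0.07–0.17 | 0.43–0.78 | 0.41 |
| 65 | 0.01–0.08 | 0.10–0.48 | 0.19 |

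The result depends almost wholly on how far the assumed mean lies above 50.

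**Step 4: effect of a baseline condition alone.** In the same simulation, counting a child only if baseline diastolic was at least 50 changes the share ever flagged as follows:

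- mean 55: 66.8% to 41.6%;
- mean 60: 40.8% to 30.7%;
- mean 65: 18.6% to 15.7%.

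These simulated children are stable by construction. The remaining flags come from ordinary variation around a limit close to their usual value. A baseline condition therefore helps but does not replace limits suited to the children.

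**Step 5: weight in the table.** SAP 3.1 expects about 20 paediatric subjects and about 100 from 998HB102. One flagged child moves the 9HB02PED column by 1/20 = 5 percentage points and the total by 1/120 = 0.8 points.

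**The case against.** The strongest reply is that little depends on this table. The protocol states in section 16: "No formal comparison is planned and no hypothesis will be formally tested". The primary endpoint, inhibitor development, is untouched. SAP 8 already reports by parent study, so the 998HB102 column is not affected by the children and no separate paediatric table need be requested. SAP 8.4 also summarises observed values and changes from baseline by visit and lists all vital signs. A reader might infer that false flags would hide a real haemodynamic change, but those other outputs, together with adverse event recording, mean the documents do not support that. All of this stands, and it limits the severity.

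A reader might also infer that the table would mostly record the normal physiology of healthy young children. The documents give no paediatric pulse or pressure values, so they cannot show this. At an assumed mean of 65 mmHg the share flagged may be only about one in ten. The illustration also holds one distribution over 8 visits, whereas the under-6 cohort is fixed in the parent study (planned for at least 50 weeks of treatment) and the children age through up to 4 further years. If diastolic pressure rises with age, the cumulative figures are too high.

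The laboratory precedent should not be overread either. Tables 2 and 3 split by parent study, not by age at measurement, and several limits, such as platelets and high haematocrit, are the same in both groups.

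None of this answers Step 1. For pulse and blood pressure, an unchanged value is counted as a post-baseline abnormality, contrary to the SAP's laboratory rule and the table's title.

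**Conclusion.** The point holds for pulse, systolic and diastolic pressure, and not for temperature. Two parts rest on the text alone: Table 4 has one set of absolute limits for all ages, and it counts values unchanged from the 9HB01EXT baseline. Both are inconsistent with SAP 8.3.1.3, and the second also with the planned title.

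The number of children affected is unknown. The range of about 10% to over 80% ever flagged rests on assumed mean diastolic values of 52 to 65 mmHg, assumed SDs and 7 to 8 visits. It shows how sensitive the count is and is not a forecast. Severity is minor, because only a descriptive safety table is affected.

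**What to change.** In SAP 8.4:

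1. For all subjects, count an absolute-limit abnormality in pulse, systolic or diastolic pressure only if it was not already present at 9HB01EXT baseline. State how a missing baseline is handled, since SAP 5.1.2 sets baseline to missing in summary tables when it falls in a major surgical/rehabilitation period. SAP 8.3.1.3 already has a rule for subjects without a baseline value that could be adopted.
2. For subjects from 9HB02PED, either add a separate, age-appropriate set of pulse and blood-pressure limits, written into the SAP before the table is run, or use only the change-from-pre-dosing criteria.

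With the first change, the absolute-limit counts match the planned title. If the change criteria keep the pre-dosing reference, a footnote should say so.

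The cost is SAP wording and programming on data already collected. The downside is that the all-ages total would rest on different limits by group and needs a footnote.
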